2.8. Methods

2.8.1. Drugs and Dosage

Upon enrollment in the study, the participant will be randomly assigned to the Low Dose or the Fully Active Dose condition. Condition assignment will be performed with a table of random numbers generated by the Institute for Statistics, University of Bern. All study investigators will remain blind to condition assignment. If there is an adverse event or other emergency requiring knowledge of participant's condition assignment, the blind may be broken for an individual participant.

Participants in the Low Dose condition are assigned to receive an initial dose of 25 mg MDMA followed 2.5 hours later by a supplemental dose of 12.5 mg MDMA. Participants assigned to the Fully Active dose condition will receive an initial dose of 125 mg followed 2.5 hours later by a supplemental dose of 62.5 mg MDMA. Eight of 12 subjects, or 66.6%, will be assigned to the Fully Active dose condition, and 4 of 12, or 33.3%, will be assigned to the Low Dose condition.

The two doses of MDMA chosen for the Low Dose condition have been selected on the basis of their ability to produce minimal but detectable subjective effects (Grob et al. unpublished; Harris et al. 2002) and thus serve as an active placebo. The cumulative dose of 37.5 mg MDMA is not expected to produce a significant reduction in anxiety or a significant increase in access to emotionally upsetting material, though this dose may produce slight alterations in consciousness, such as increased relaxation or tension (Harris et al. 2002). The initial 125 mg dose of MDMA selected for the Fully Active Dose condition was chosen on the basis of case reports of MDMA-assisted psychotherapy conducted in the US prior to scheduling (Greer and Tolbert 1986), as well as on data obtained from [name] MAPS-sponsored MDMA/PTSD pilot study currently underway in the United States. This dose is expected to reduce fear in response to emotionally upsetting thoughts, feelings or memories and to increase access to emotionally intense material, and is thus expected to be therapeutically active. Doses equal to or exceeding 125 mg have been employed in previous uncontrolled and controlled studies of MDMA (Cami et al. 2000; Grob et al. 1996; Grob et al. Unpublished; Harris et al. 2002; Lester et al. 2000; Mas et al. 1999; Styk 2007; Tancer et al. 2001; Tancer et al. 2003; Vollenweider et al. 1998).

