Statistical significance will be set at 0.05. Because the sample size is very small, the study has sufficient power only to detect large effects. Therefore, there will be no adjustment for multiple testing; p-values and confidence intervals will be reported instead. We will assess participant CAPS and PDS scores at baseline and two months after each participant has undergone a final session, defined as the last experimental or open-label MDMA-assisted psychotherapy session, using the same nonparametric tests employed in comparisons of active placebo and experimental dose MDMA described above.

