Time: Baseline, 2, months after Stage 1 or Stage 2 Experimental Session 3, 6 months after Stage 1 or Stage 2 Experimental Session 3, 12 months after Stage 1 or Stage 2 Experimental Session 3.

Demographic factors analysis

Goal: To test for a main effect of the basic demographic factors gender, age, number of years of psychotherapy and presence of additional affective disorders upon PTSD symptoms across both conditions, meeting PTSD diagnostic criteria, and reduced psychological symptoms and three weeks after 3rd Stage 1 experimental session

Population: Intention to treat, Per protocol

Data included in analysis: CAPS (Global Score and subscales, Diagnostic criteria met, Associated Features) and PDS (Severity Score, Rating, Impairment). Demographic variables will include gender, age, years of psychotherapy, presence of other affective disorder.

Format of analysis: Repeated-measures ANOVA for categorical data (gender, presence of additional affective disorder), linear regression for continuous data (age, years of psychotherapy)

Time: Baseline, End of Stage 1

Between group factors / independent predictors: Gender, age, years of psychotherapy, presence/absence of other affective disorder

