6.4.3 Subsidiary analyses

Goal: To test for the source of variance of any potential interactions between demographic variables and outcome measures. These analyses will only be performed if any interactions are

found between specific criteria and efficacy data. NOTE: if there are no significant findings for given score, will not perform subsidiary analysis on specific score.

Population: Intention to Treat and Per Protocol

Data included in analyses: CAPS (Global Score and specified subscales, Diagnostic criteria met, Associated Features), PDS (Severity Score, Rating, Impairment)

If and only if there are systematic differences detected by chi square in a demographic variable (age, gender, # years psychotherapy).

Format of Analyses: A) Repeated measures analysis of variance using condition and demographic variable as between group variable and time of administration as repeated measure OR B) two separate repeated measures analyses of variance with condition as a between-group factor, one analyses with and one without members of specific category.

Time: Baseline, 3 weeks after 2rd Stage 1 experimental session, 3 Weeks After 3rd Stage 1 Experimental Session

Between-groups factors: Condition (125 mg MDMA, 25 mg MDMA); Demographic factor (e.g. male, female)

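### The demographic factors analysis (SAP 6.4.2) omits randomised condition, so any drug effect inflates its error term and, under chance imbalance, biases the demographic estimate

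*SAP*

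**What the plan says.** SAP 6.4.2, under the demographic factors analysis, sets out to test demographic effects "upon PTSD symptoms across both conditions". Categorical factors go into a repeated-measures ANOVA and continuous ones (age, years of psychotherapy) into a linear regression. The time points are given as "Time: Baseline, End of Stage 1" and the predictors as "Between group factors / independent predictors: Gender, age, years of psychotherapy, presence/absence of other affective disorder". Condition appears in neither model, although the main analysis in 6.4.1 and Additional analyses #1 to #3 all list it as the between-group factor. Nothing has to be met before this analysis is run.

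SAP 6.4.3, Subsidiary analyses, is a separate section. Its option A is the only planned efficacy model with condition and a demographic variable as factors together; option B runs condition-only models with and without a category of patients. Three triggers are written there: an interaction between a demographic variable and the efficacy data has been found; the score in question has a significant finding; and "If and only if there are systematic differences detected by chi square in a demographic variable", where the variables named are age, gender and years of psychotherapy. The section does not say what the variable is compared across. I read it as condition, which is how the parallel safety analysis in 6.5.2 is worded.

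**The concern.** The trial expects a drug effect, and Protocol 2.8.3 says that "the study has sufficient power only to detect large effects". A large drug effect is also the setting in which leaving condition out does most harm. With 8 patients on full dose and 4 on low dose, the pooled outcome is a mixture of two distributions. A model that knows only sex or age treats the gap between them as noise. If the factor happens to be unevenly spread over the arms, part of the gap is credited to the factor or subtracted from it.

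What is at stake is whether a real predictor of response is missed, or a chance one reported, in a 12-patient data set that already holds the variable needed to prevent this. The 6.4.3 model that would separate the two effects may never be run, because of its triggers.

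**Working it through.** **Inputs from the documents.** N = 12, allocated 8:4 (Protocol 2.8.1). Significance level 0.05 (Protocol 2.8.3). Predictor list and two time points (SAP 6.4.2). The plan gives no power or error-rate figure for this analysis, so there is none to reproduce.

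**Assumptions.** Two-sided tests. Drug effect *d* of 1 to 2.5 within-group SDs of the change score. A sex effect of 1.9 SD where power is shown. Sex splits as stated below. None of these is in the documents. The test is sex on the change from baseline to end of Stage 1, which equals the sex-by-time test of a two-time repeated-measures ANOVA. Rates come from simulation, at least 40,000 data sets per setting, with 10 residual df without condition and 9 with it.

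**Step 1: noise.** Ignoring condition, the residual variance is σ² + *d*²σ² × (8/12)(4/12), a multiplier of 1 + (2/9)*d*². This is 1.22 at *d* = 1, 1.50 at 1.5, 1.89 at 2 and 2.39 at 2.5.

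**Step 2: bias.** The sex contrast is shifted by *d* × (full-dose share among women − full-dose share among men). For women in 4/8 of the full-dose arm and 4/4 of the low-dose arm, this is *d* × (4/8 − 4/4) = −0.50*d*. For women 2/8 v 3/4, it is *d* × (2/5 − 6/7) = −0.46*d*. It is zero for women 4/8 v 2/4.

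**Step 3: rejection rates without condition.**

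| *d* | Balanced (4/8 v 2/4), no sex effect | Balanced, power for 1.9 SD | 4/8 v 4/4, no sex effect |
|---|---|---|---|
| 1 | 3.1% | 77% | 8.5% |
| 1.5 | 1.6% | 68% | 11% |
| 1.9 | 0.9% | 58% | 13% |
| 2.5 | 0.3% | 40% | 15% |

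With condition in the model, the columns are about 5%, 83% and 5% at every *d*. For women 2/8 v 3/4 at *d* = 1.9, error is about 11% without condition and 5% with it. Imbalance can also hide a real effect: at 4/8 v 4/4, *d* = 1.9 and a 1.9 SD sex effect in the same direction as the drug effect, power is 13% without condition and 67% with it.

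**Step 4: average over randomisation.** Averaged over all 8:4 allocations rather than conditional on one, type I error without condition is about 5% (4.6% to 5.8% over the splits and effects tried). The conservative balanced allocations offset the anti-conservative imbalanced ones.

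**Step 5: the chi-square trigger in 6.4.3.** For 4/8 v 4/4, X² = 12 × (4×0 − 4×4)² / (8×4×8×4) = 3.00, p = 0.083. For 2/8 v 3/4, X² = 12 × (2×1 − 6×3)² / (8×4×5×7) = 2.74, p = 0.098. Neither passes 0.05, although these are the allocations in which error is 11% to 13% at *d* = 1.9. Enumerating all allocations, Pearson chi-square falls below 0.05 in 0% (sex split 1/11), 9.1% (2/10), 1.8% (3/9), 6.7% (4/8), 8.1% (5/7) and 6.1% (6/6) of them; with the Yates correction or Fisher's exact test, in 0% to 1.8%. The smallest expected count in the 4/8 v 4/4 table is 4 × 4/12 = 1.33, so the chi-square approximation is itself doubtful. Age and years of psychotherapy are continuous in 6.4.2, so chi-square would need cut-points that the SAP does not give.

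**Step 6: the other possible test.** The stated goal in 6.4.2 is a main effect. If that means the between-subject effect averaged over the two times, it carries *d*/2. Assuming equal variances and a within-subject correlation of 0.5, the SD of that average is √0.75 of the change-score SD. At *d* = 1.9, error at 4/8 v 4/4 is then about 9% against 5%, and balanced power is 30% against 40%.

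**The case against.** A reader who puts 6.4.2 and 6.4.3 together might infer that the demographic tests are themselves gated by chi-square. They are not. The 6.4.2 tests are ungated; the trigger belongs to 6.4.3, whose models do contain condition, and it stands beside two other triggers. A reader might also infer that a working drug will regularly show up as a sex or age effect. Randomisation makes the factors independent of arm in expectation, and Step 4 bears that out. The raised error rates are conditional on a chance imbalance, and with balanced sexes the test is too conservative. Both corrections stand. They leave the loss of power untouched, since that needs no imbalance, and the trial will analyse one realised allocation of 12 people, not the average.

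The effect sizes are assumed. At *d* = 1 the balanced loss is only 77% against 83%, and Step 6 shows smaller losses for the averaged main effect. That stands, which is why a range is given. Only sex was simulated; the same algebra applies to a continuous factor, but no figure is offered for age. Nor does 6.4.2 say whether the four predictors enter singly or together; condition is absent either way.

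Adding condition is not free. If the drug has no effect, power for a 1.9 SD sex effect falls from about 84% to 83% when balanced, but from 80% to 67% at 4/8 v 4/4, because sex and condition are then correlated. This is a real cost, and larger than one degree of freedom suggests.

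Finally, these are additional and subsidiary analyses in a 12-patient pilot and would be hypothesis-generating under either model. That is right, and it sets the weight of the point. The documents do not say that demographic predictors will be carried into later trials.

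**Conclusion.** The point holds as a cheap improvement to a secondary analysis. SAP 6.4.2 leaves randomised condition out of its demographic models. The drug effect then inflates residual variance by 1.22 to 2.39 times over *d* = 1 to 2.5. It also biases the demographic estimate in any allocation where the factor is imbalanced, with no systematic inflation of error over repeated randomisation. On a change score the power loss with balanced sexes runs from about 6 points (*d* = 1) to 43 points (*d* = 2.5) for an assumed 1.9 SD sex effect, and is smaller for the averaged main effect.

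The route to a model with both condition and a demographic factor is a separate weakness. A 6.4.2 model without condition cannot show a demographic-by-condition interaction, and the chi-square trigger tests imbalance that randomisation has already made a matter of chance, with almost no sensitivity at 8 v 4.

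It would be wrong to infer that the trial's efficacy conclusion is at risk: the comparison in 6.4.1 contains condition and is unaffected.

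**What to change.** In SAP 6.4.2, add condition as a between-group factor in each demographic repeated-measures ANOVA and as a covariate in each demographic regression. State whether the factor-by-time effect or the effect averaged over time is the one of interest. In 6.4.3, remove the chi-square imbalance trigger. The interaction and significance triggers can stay, but the SAP should say which model the interaction is to be found in. Label the results of both sections exploratory.

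The change needs no new data. It costs one of ten residual degrees of freedom, plus the loss of power described above if the drug has no effect and the factor is imbalanced.

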6.4.3 Subsidiary analyses

Goal: To test for the source of variance of any potential interactions between demographic variables and outcome measures. These analyses will only be performed if any interactions are

found between specific criteria and efficacy data. NOTE: if there are no significant findings for given score, will not perform subsidiary analysis on specific score.

Population: Intention to Treat and Per Protocol

Data included in analyses: CAPS (Global Score and specified subscales, Diagnostic criteria met, Associated Features), PDS (Severity Score, Rating, Impairment)

If and only if there are systematic differences detected by chi square in a demographic variable (age, gender, # years psychotherapy).

Format of Analyses: A) Repeated measures analysis of variance using condition and demographic variable as between group variable and time of administration as repeated measure OR B) two separate repeated measures analyses of variance with condition as a between-group factor, one analyses with and one without members of specific category.

Time: Baseline, 3 weeks after 2rd Stage 1 experimental session, 3 Weeks After 3rd Stage 1 Experimental Session

Between-groups factors: Condition (125 mg MDMA, 25 mg MDMA); Demographic factor (e.g. male, female)

6.5 Safety Analysis

Population: All enrolled, intention to treat, per protocol, partial crossover, Extended Assessment 1 (when applicable), Extended Assessment 2 (when applicable)

Categorical data includes: Spontaneously reported reactions occurring seven days after an experimental session (maximum intensity, duration within 24 hrs of the experimental session, total duration across seven days), Adverse Events

Format of presentation: Summary tables of frequency listings in total, by condition (placebo, MDMA, partial crossover, Extended Assessment 1, Extended Assessment 2), by relatedness to study drug, by session number, by body system, by classification

Content of presentation: Specific spontaneously reported reactions by classification (across 7 days after an experimental session), number of spontaneously reported reactions, Adverse Events

Descriptive data includes: Physiological data (vitals, vital signs above cut-off and time point above cut-off during experimental sessions); psychological distress (SUD); Lab values

Format of presentation: Summary tables of frequency listings in total, by condition and by session number when applicable.

Content of presentation: Pre-drug average, maximum change (peak), and post-drug average values of physiological data (HR, SBP, DBP, BT); vital signs above cut-off and time point above cut-off during experimental sessions; psychological distress (SUD)

6.5.1 Main Analysis

Physiological Measures and SUD

Analysis #1

Goal: to test the presence of a main effect of condition (125 mg MDMA, 25 mg MDMA, 150 mg MDMA in Extended Assessment 2) on changes in vital signs and psychological distress,

Population: All enrolled, intention to treat, per protocol, partial crossover, Extended Assessment 2

Data included: Pre-drug average, maximum change (peak) and post-drug average SBP, DBP, HR, BT and SUD, number of participants with vital signs above clinical cut off and duration above clinical cut-off

Format of Analyses: One-way ANOVA per each experimental session, including sessions during Stage 1, Stage 2 and Stage 3

Between-Group Factor: Condition (125 mg MDMA, 25 mg MDMA, 150 mg MDMA in Extended Assessment 2)

Analysis #2

Goal: To test effects of condition, presence or absence of supplemental dose and time of session on physiological data and psychological distress during experimental sessions

Population: All enrolled, intention to treat, per protocol

Data included: Pre-drug average, maximum change (peak) and post-drug average SBP, DBP, HR, BT and SUD, number of participants with vital signs above clinical cut off.

Format of analysis: Repeated measures ANOVA

Time: Session (Experimental 1, Experimental 2, Experimental 3)

Between Groups Factors: Condition (125 mg MDMA, 25 mg MDMA) as between-group factor, and supplemental dose (given, not given) as second between-group factor.

Analysis #3

Goal: To test effects of condition, presence or absence of supplemental dose and time of session on physiological data and psychological distress during Stage 2 or Stage 3 sessions.

Population: Partial crossover, Extended Assessment 2

Data included: Pre-drug average, maximum change and post-drug average SBP, DBP, HR, BT and SUD, number of participants with vital signs above clinical cut off, and duration above clinical cut-off.

Format of analysis: Repeated measures ANOVA

Time: Crossover Session (Stage 2 Experimental Session 1, 2, and 3, Stage 3 Experimental sessions 1 and 2)

Between-Subjects factors: Supplement (present, absent)

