
Blood pressure, pulse and temperature will be measured according to Table 3. The exact timing will be at the discretion of the therapists so that testing will not interfere unnecessarily with the therapeutic process.

Approximately 2.5 hours later, the therapist-investigators will offer the participant the supplemental dose of MDMA. They will only do so if, in their judgment, the participant does not show any signs or symptoms suggesting that an additional dose of MDMA could produce a serious adverse event. If the participant agrees to take the supplemental dose, then it will be administered with 250 to 300 mL electrolyte-containing beverage. All experimental sessions will be audiotaped in their entirety.

Sessions will last from six to eight hours, depending on when the participant feels that he or she has arrived at a point of completeness with the process and on dependent the therapists' determination of the mental and physical state of the participant. Participants will receive a copy of the experimental session recording as soon as one is available.

Table 3. Schedule of Procedures and Measures for Experimental Sessions

TIME	Procedure or Action
9:00	Urine drug screen and pregnancy test. Participant acclimated to environment
9:45	Baseline BP, Pulse, Temp, Subjective Units of Distress Rating (SUDS)
9:55	2 nd Baseline BP, Pulse, SUDS
10:00	Drug Administration, begin audiotaping
10:30	BP, Pulse.
11:00	BP, Pulse, Temp, SUDS
11:30	BP, Pulse
12:00	BP, Pulse, Temp
12:30	BP, Pulse, SUDS
13:00	BP, Pulse, Temp
13:30	BP, Pulse,
14:00	BP, Pulse, Temp, SUDS
Every hour, and as needed	BP, Pulse,
Every 60-90 minutes	SUDS, Temp

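### SAP 6.5.1 compares the post-drug average of vital signs and SUD between doses without using the same session's pre-drug average, and leaves maximum change (peak) undefined: a minor loss of precision if pre- and post-drug values correlate well

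*SAP*

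**What the plan says.** SAP 6.5.1 Analysis #1 tests for an effect of condition "on changes in vital signs and psychological distress". Its outcomes are given as "Data included: Pre-drug average, maximum change (peak) and post-drug average SBP, DBP, HR, BT and SUD", together with counts and durations above clinical cut-off. The model is stated as "Format of Analyses: One-way ANOVA per each experimental session, including sessions during Stage 1, Stage 2 and Stage 3", with condition as the only factor.

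Analysis #2 takes the same three summaries into a repeated-measures ANOVA. Its repeated factor is session number, not pre-dose against post-dose: "Time: Session (Experimental 1, Experimental 2, Experimental 3"). Its other factors are "Condition (125 mg MDMA, 25 mg MDMA) as between-group factor, and supplemental dose (given, not given) as second between-group factor". Neither analysis names a covariate.

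Protocol 2.8.5.1, Table 3, schedules two pre-dose readings in every experimental session:

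- 9:45: "Baseline BP, Pulse, Temp, Subjective Units of Distress Rating (SUDS")
- 9:55, the second baseline: "Baseline BP, Pulse, SUDS"
- 10:00: "Drug Administration, begin audiotaping"

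Blood pressure, pulse and SUDS thus have two readings, nominally 15 and 5 minutes before dosing. Temperature has only the 9:45 reading. The protocol lets the therapists vary the exact times.

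**The concern.** A raw post-drug average does not measure change. It carries each person's resting level, so between-person spread in resting blood pressure, pulse and temperature stays in the error term. SAP 1.0 defines difference scores, but 6.5.1 does not apply them to this outcome. The pre-drug average appears instead as an outcome in its own right. In session 1, testing it by condition checks the randomisation and says nothing about the drug.

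Vital signs and SUD are the measures named in the safety objectives (SAP 3.3). With 8 v 4 participants, Protocol 2.8.3 accepts that only large effects can be detected. If resting values predict post-drug values well, the unadjusted comparison gives a wider interval than the data need, and a real difference between doses is more likely to come out as non-significant.

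The same list leaves maximum change (peak) open. It could be the raw maximum, or the maximum minus the pre-drug value. Analysis #3 in 6.5.1 says only maximum change, and 6.5.2 says only peak. Whether that outcome uses the baseline depends on which is meant.

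**Working it through.** The documents give no effect size, SD, correlation or power figure for these analyses, so there is no stated figure to reproduce.

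**Inputs**

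- 8 full dose v 4 low dose, N = 12 (Protocol 2.8.1).
- Significance level 0.05 (Protocol 2.8.3). Sidedness is not stated; two-sided is assumed.
- Equal pre- and post-drug SD, and a true difference of 1.5 SD: assumptions.
- Pre/post correlation r: an assumption, shown over a range.

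**Formulas, single Stage 1 session, variance relative to the raw comparison**

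- Raw post-drug value: 1, with 10 error df.
- Change score: 2(1 − r), 10 df.
- ANCOVA: (1 − r²) × [1 + 1/(N − 4)] = (1 − r²) × 1.125, 9 df.

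Power comes from the noncentral t distribution. For the raw comparison the noncentrality is 1.5 × √(8 × 4/12) = 1.5 × 1.633 = 2.45, which gives power 0.60. For ANCOVA it is divided by the square root of the variance ratio. At r = 0.7 the ratio is 0.51 × 1.125 = 0.574, the noncentrality is 2.45/√0.574 = 3.23, and power is 0.82.

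| r | Variance ratio, ANCOVA | CI width ratio, ANCOVA | Power, ANCOVA | Variance ratio, change score | Power, change score |
|---|---|---|---|---|---|
| 0 | 1.125 | 1.08 | 0.54 | 2.00 | 0.35 |
| 0.3 | 1.02 | 1.03 | 0.58 | 1.40 | 0.47 |
| 0.5 | 0.84 | 0.93 | 0.66 | 1.00 | 0.60 |
| 0.6 | 0.72 | 0.86 | 0.73 | 0.80 | 0.70 |
| 0.7 | 0.57 | 0.77 | 0.82 | 0.60 | 0.81 |
| 0.8 | 0.41 | 0.65 | 0.93 | 0.40 | 0.94 |

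The effect detectable with 80% power is 1.90 SD for the raw comparison. With ANCOVA it is 1.77, 1.64, 1.46 and 1.23 SD at r = 0.5, 0.6, 0.7 and 0.8.

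**Break-even.** The variance is equal when (1 − r²) × 9/8 = 1, so r² = 1/9 and r = 0.33. Allowing also for the lost degree of freedom, the interval widths are equal at r = 0.37.

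**Check.** Simulation of 40,000 trials per value of r (0, 0.3, 0.5, 0.7 and 0.8) agreed. ANCOVA variance ratios were 0.83, 0.58 and 0.41, and power 0.67, 0.82 and 0.93, at r = 0.5, 0.7 and 0.8.

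These figures fit only a single-session, two-group Stage 1 model. They do not carry over to the Stage 2 and Stage 3 sessions in Analysis #1, where the comparison is not the randomised 8 v 4, or to Analysis #2, which has a second between-group factor and three sessions.

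**The case against.** The strongest reply is that the plan partly deals with this already. The goal of Analysis #1 speaks of changes, and the natural reading of maximum change is peak minus pre-drug. On that reading the table leaves ANCOVA almost nothing to add at r = 0.7 (power 0.82 v 0.81) and nothing at r = 0.8 (0.93 v 0.94). This stands. A reader might infer that every post-drug comparison ignores the baseline; the documents support that only for the post-drug average. What remains for the peak is a missing definition.

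Second, r is not in the documents. A reader might infer that the plan certainly throws precision away, but that needs r above about 0.33 to 0.37. It is plausible for same-day blood pressure and pulse. It is less certain for peaks under drug, and for SUD, a one-item 1-7 rating (Protocol 2.8.2) taken in sessions meant to bring up distressing material. This also stands.

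Third, a reader might infer that the unadjusted result is biased, or that it would conceal a rise. Neither follows. Under randomisation the unadjusted Stage 1 contrast is unbiased, and its standard error allows for chance imbalance. SAP 6.5 also reports values and times above cut-off and tables by condition and session. Monitoring of individuals rests on the thresholds in Protocol 2.8.8, not on an ANOVA.

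Fourth, ANCOVA assumes a linear, common slope, which cannot be checked with four low-dose participants. Protocol 2.8.3 makes the like point about parametric assumptions for CAPS and PDS. This is a fair cost and a reason to keep the unadjusted result in view.

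**Conclusion.** The point holds in a narrow form. In Analyses #1 and #2 the post-drug average of the four vital signs and SUD is compared between doses without that session's pre-drug average, although the stated aim is change and the readings are already scheduled. Maximum change (peak) needs a definition.

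The size depends on the assumed r. Between 0.5 and 0.8 the variance of the Stage 1 comparison falls by 16% to 59% and the confidence interval narrows by 7% to 35%. Below about 0.33 to 0.37 there is a slight loss. The power figures also rest on the assumed 1.5 SD effect and equal SDs.

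This is a minor precision improvement to a safety analysis. It corrects no bias in the randomised comparison and does not affect CAPS.

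**What to change.** In SAP 6.5.1:

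1. State whether maximum change (peak) is the raw peak or peak minus pre-drug, and use one term in 6.5.1 and 6.5.2.
2. For the Stage 1 randomised comparison, analyse the post-drug average (and the peak, if raw) in each session by ANCOVA with that session's pre-drug average as covariate. Report the adjusted 125 mg minus 25 mg difference with a 95% CI beside the unadjusted one. Showing both matters because SAP 8.0 records that preliminary data had already been presented.
3. For Analysis #2, use a mixed model that accepts the session-specific pre-drug value. The covariate varies by session, which the named repeated-measures ANOVA does not provide for.
4. Keep the session 1 pre-drug average descriptive. In sessions 2 and 3 it follows earlier dosing, so the adjusted contrast is the acute within-session effect. Still report those pre-drug values by condition, so that any carry-over or anticipatory distress can be seen.

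Cost: SAP wording and no new data. In the single-session model it takes one error degree of freedom of ten and adds the common-slope assumption, with a small loss of precision where r is low, which is possible for SUD. Analysis #2 also needs a change of model.
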